**Table JBAS.12.1. Summary of Historical Trials**

Trial Name	Sample Size	Median OS (Months)	Hazard Rate (per Week)
Cheng et al. 2009	150	6.5	0.02666
Cheng et al. 2011	410 (Asian Pacific subgroup)	8.8	0.0197
Weighted overall	560	8.2	0.0216

Abbreviation: OS = overall survival.

- A fixed prior distribution for the sorafenib plus placebo hazard rate following a gamma distribution with a mean of 0.0216/week and a weight of 10 (strong prior) and a weight of 1 (weak prior);
- The prior distribution of the log HR between the combination arm and the control arm is assumed to be normally distributed with a mean of 0 and a standard deviation of 100 (weak prior);
- True HRs between the combination arm and the control arm, LY2157299 monotherapy arm and the control arm, are 0.667 and 1, respectively;
- The accrual rate is 10 patients/month (1.7 patients/week);
- The minimum follow-up for the last patient is approximately 2 years (104 weeks).

The simulations indicate that, by randomizing 120 patents, the posterior probability of concluding superiority of the combination arm over the control arm is approximately 83%

(strong prior) and 74% (weak prior) (Table JBAS.12.2). Assuming an HR of 1, the posterior probability of concluding superiority of the combination arm over the control arm (ie, type I error) is approximately 14% to 15%. For comparison purpose, a frequentist analysis using the log-rank test would give a power of 73% assuming the HR = 0.667 and type I error = 14% (one-sided).

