**Table JBAS.5.1. Sorafenib in Asian Populations**

Study	Sample Size (Number of Patients)	Median OS (Months)	Reference
Sorafenib versus placebo	150	6.5	Cheng et al. 2009
Sorafenib versus sunitinib	410 (Asian Pacific subgroup)	8.8	Cheng et al. 2011
Sorafenib versus brivanib	372 (Asian subgroup)	8.9	Johnson et al. 2013

Abbreviation: OS = overall survival.

Transforming growth factor beta (TGF- $\beta$ ) has been shown to be a tumor promoter in advanced, metastatic cancer; while in normal tissue, TGF- $\beta$  inhibits epithelial cell proliferation (de Caestecker et al. 2000; Massagué et al. 2000; Derynck et al. 2001; Wakefield and Roberts 2002). Because of this tumor-promoting activity, TGF- $\beta$  inhibition is currently being considered as a treatment option in patients with advanced cancer (Yingling et al. 2004).

TGF- $\beta$  signals into the cell by engaging TGF- $\beta$  receptor type I (RI) and type II and inducing phosphorylation of the TGF- $\beta$  receptor kinases (Shi and Massagué 2003). The TGF- $\beta$  RI kinase phosphorylates SMAD2 and SMAD3, resulting in the formation of SMAD complexes, which are subsequently translocated into the nucleus to stimulate gene transcription of TGF- $\beta$  responsive genes (Derynck et al. 2001). Therefore, assessment of phosphorylated SMAD (pSMAD) after TGF- $\beta$  activation can be used to determine the ability of the host to respond to TGF- $\beta$  activation.

Several mechanisms have been proposed to explain the tumor-promoting activity of TGF- $\beta$ , such as increased neovascularization of the tumor causing increased nourishment to the tumor cells, immunosuppression leading to the escape of tumor immune surveillance, and increased migration and invasion resulting in metastasis (Akhurst and Derynck 2001; Derynck et al. 2001; Siegel and Massagué 2003). These combined effects on the tumor microenvironment by TGF- $\beta$  promote tumor progression, and therefore a TGF- $\beta$  RI kinase inhibitor is expected to cause arrest of tumor growth and metastasis in patients.

It has been reported that TGF- $\beta$ 1 is increased in HCC patients and correlates with worst prognosis. In addition, plasma TGF- $\beta$ 1 levels are elevated in HCC patients with alpha-fetoprotein (AFP) levels above 10 IU/mL (Sacco et al. 2000).

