## 12. Sample Size and Statistical Methods

### 12.1. Determination of Sample Size

Approximately 150 patients will be entered into this study in order that 120 patients will be randomly assigned to 1 of 3 treatment arms. The randomization will be in a 1:2:1 allocation ratio with 30 patients in LY2157299 monotherapy, 60 patients in LY2157299 plus sorafenib therapy, and 30 patients in sorafenib plus placebo therapy.

The primary objective is to compare the OS distributions between LY2157299 plus sorafenib therapy (combination arm) with sorafenib plus placebo (control arm) using a Bayesian augmented control design. By incorporating historical information regarding the control group into the Bayesian model, it is possible to improve the operating characteristics compared to a standard (frequentist) analysis. The primary objective will be considered to be met if, after 120 patients have completed at least 2 years of follow-up, the posterior probability is >84% that the HR for OS of the combination arm versus control arm is <1.

The study is designed to observe approximately 100 deaths. Simulations (FACTS version 3.2) were carried out using below assumptions:

- Exponential survival model using summary hazard rates from 2 previous sorafenib trials in Asia-Pacific population (see [Table JBAS.12.1](#)), along with data from the sorafenib plus placebo arm in this study;

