### **12.2.6. Primary Outcome and Methodology**

OS duration will be measured from the date of randomization to the date of death from any cause. For each patient who is not known to have died as of the data-inclusion cut-off date for a particular analysis, OS will be censored for that analysis at the date of last contact prior to the

data inclusion cut-off date. (Contacts considered in the determination of last contact date include AE date, lesion assessment date, visit date, and last known alive date.) A method of analysis for comparing OS between the treatment arms will use a Bayesian exponential-likelihood model with possibly a hierarchical random-effects distribution on treatment effects. The model incorporates historical data from 2 studies with a sorafenib plus placebo arm to augment the prospective control arm data. If the Bayesian posterior probability of superiority of the combination arm over the control arm (ie, HR <1) exceeds 0.84 under a strong prior, then it will be concluded that the combination arm is superior. The same analysis will be repeated using the weak prior. A similar Bayesian analysis will be carried out to provide 90% predictive intervals of the HR between the control arm and LY2157299 monotherapy.

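### Under the strong prior that decides the primary analysis, the stated 14% type I error holds only near a control hazard of 0.0216 per week, which is a median of about 7.4 calendar months, not 8.2

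*Protocol*

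**What the plan says.** The primary comparison has "60 patients in LY2157299 plus sorafenib therapy, and 30 patients in sorafenib plus placebo therapy" (protocol 12.1). The objective is met if "the posterior probability is >84% that the HR for OS of the combination arm versus control arm is <1". Protocol 12.2.6 and SAP 6.9.1 fix the prior for that decision: the combination is declared superior if the probability "exceeds 0.84 under a strong prior, then it will be concluded that the combination arm is superior". The weak prior is used only for a repeat analysis.

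The historical information enters as "A fixed prior distribution for the sorafenib plus placebo hazard rate following a gamma distribution with a mean of 0.0216/week", with "a weight of 10 (strong prior) and a weight of 1 (weak prior"). The mean is the sample-size-weighted average of two trial hazards in protocol Table JBAS.12.1: 0.02666 (median 6.5 months, 150 patients) and 0.0197 (median 8.8 months, 410 patients). The pooled row gives 8.2 months and 0.0216 per week.

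For a true HR of 1 the documents say that the "type I error) is approximately 14% to 15" percent, which is one figure per prior: 14% strong and 15% weak (protocol Table JBAS.12.2, SAP Table JBAS.5.2). They do not say which true control hazard was simulated, and they show no result for a control hazard away from the prior mean. Protocol Table JBAS.5.1 lists a third Asian sorafenib dataset, "372 (Asian subgroup"), with a median of 8.9 months, which is not in the prior.

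**The concern.** A fixed gamma prior keeps its full weight however far the concurrent control arm departs from it. If control patients live longer than the prior assumes, the prior pulls the estimated control hazard up and an inactive combination looks better than control. If they live shorter, the error moves the other way. A single figure therefore describes one point on a curve.

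Protocol 12.2.6 mentions a possible hierarchical random-effects distribution on treatment effects, but SAP 6.9.1 drops it. The SAP thus specifies nothing that lets the data discount the history.

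The place of the prior mean on that curve depends on the month-to-week conversion, and the tabulated hazards come from a 4-week month. The superiority claim rests on 30 concurrent controls and is meant to inform Phase 3, so readers need to know how far its false-positive rate can move.

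**Working it through.** **Inputs.** Arms 30/60/30, threshold 0.84, exponential survival, prior mean 0.0216 per week, weights 10 and 1, log HR prior N(0, SD 100), about 100 deaths, 104 weeks of minimum follow-up, accrual 1.7 per week (all protocol 12.1). The protocol equates 1.7 per week with 10 per month; the weekly figure is used here because it reproduces the stated timings. Weight is read as equivalent events, which is an assumption.

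**Model.** With d deaths and T patient-weeks per arm (c = control, t = combination):
- control hazard ~ Gamma(w + d_c, w/0.0216 + T_c)
- combination hazard ~ Gamma(d_t, T_t), since the log HR prior is effectively flat
- P(HR < 1) = P(B < T_t / (T_t + w/0.0216 + T_c)), with B ~ Beta(d_t, w + d_c)

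Monte Carlo with 180,000 or more trials per cell.

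**Reproducing the plan at a true control hazard of 0.0216 per week**

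| Quantity | Stated | Cut at 100 deaths | Cut at 104-week follow-up |
|---|---|---|---|
| Type I error, strong | 14% | 13.3% | 13.6% |
| Power, strong | 83% | 80.9% | 83.3% |
| Type I error, weak | 15% | 15.3% | 15.6% |
| Power, weak | 74% | 74.7% | 77.3% |

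A calendar month is 365.25/12/7 = 4.348 weeks. Under HR 0.667 the 100th death falls at 141.3 weeks, and 141.3/4.348 = 32.5 months (stated 32.7). The 70th falls at 88.6 weeks, and 88.6/4.348 = 20.4 months (stated 20.4). At 0.0194 per week the same two times are 35.1 and 21.6 months. With accrual of 2.3 per week and 4-week months they are 32.6 and 19.4, so the pair fits less well. The stated figures therefore point to 0.0216 per week as the simulated truth, with timings in calendar months.

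**The month conversion**
- Protocol: ln2/(6.5 × 4) = 0.02666; ln2/(8.8 × 4) = 0.0197; (150 × 0.02666 + 410 × 0.0197)/560 = 0.0216.
- Median at 0.0216 per week: ln2/(0.0216 × 4.348) = 7.4 calendar months.
- Calendar months: ln2/(6.5 × 4.348) = 0.0245; ln2/(8.8 × 4.348) = 0.0181; (150 × 0.0245 + 410 × 0.0181)/560 = 0.0198.

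**Moving only the true control hazard** (weight 10 unless marked weak; first type I column is the 100-death cut / 104-week cut, other columns the 100-death cut)

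| True control median, calendar months (hazard per week) | Type I, prior 0.0216 | Power, prior 0.0216 | Type I, weak prior | Type I, prior 0.0198 | Power, prior 0.0198 |
|---|---|---|---|---|---|
| 6.5 (0.0245) | 9.4% / 9.6% | 76% | 15% | 7% | 72% |
| 8.2 (0.0194) | 16.8% / 17.1% | 84% | 16% | 14% | 82% |
| 8.8 (0.0181) | 19.4% / 19.7% | 86% | 16% | 16% | 84% |
| 8.9 (0.0179) | 20.0% / 20.2% | 86% | 16% | 17% | 84% |

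On the protocol's 4-week hazards with the prior at 0.0216, strong-prior type I error is 7.2% / 7.4% at 0.02666, 16.4% / 16.7% at 0.0197, and 16.9% / 17.3% at 8.9 months (0.0195).

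**The case against.** Dependence on the true control rate comes with any informative prior. This one is modest: 10 events against about 25 expected control deaths under HR 1, drawn from 560 historical patients, in a Phase 2 screen. The error also falls below 14% if controls do worse. The weak-prior repeat is planned (protocol 12.2.6, SAP 6.9.2.1), as are Kaplan-Meier and proportional hazards analyses without historical data. All of this stands, and it is why the point concerns what is stated rather than the borrowing itself. None of it tells the reader how far the 14% moves.

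The 20% figure also needs calendar months. On the protocol's 4-week convention the top is about 17%, and a median of 8.2 months, at ln2/(8.2 × 4) = 0.0211 per week, gives about 14%. But the plan's own analysis timings fit calendar months.

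Four stronger readings are not supported:
- A reader might infer that both quoted figures fail. The weak-prior 15% stays at about 15% to 16% over the listed medians.
- A reader might infer that the third dataset was left out to favour the combination. The documents give no reason either way, and the 8.8-month dataset is already in the prior. Most of the shift is the unit: calendar conversion takes the mean from 0.0216 to 0.0198, and adding the third dataset takes it only to 0.0191. On 4-week months, adding it gives 0.0207.
- A reader might treat 0.0191 as the right mean. It uses 410 and 372 as weights, and the table does not say whether these count sorafenib patients or whole subgroups.
- A reader might cite the 10.7-month median from the US/EU sorafenib trial in protocol Section 5, which would give about 27%. That lies outside the study region.

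**Conclusion.** The point holds for the strong prior. Its 14% is a value near the prior mean. With the prior as written, type I error runs from about 9% to 20% over the Asian sorafenib medians that the protocol lists, in calendar months, or about 7% to 17% on its 4-week hazards. At the protocol's own pooled median of 8.2 calendar months it is about 17%. At the 8.8 and 8.9 months of the two larger datasets, an inactive combination would be declared superior in about 1 trial in 5, against the 1 in 7 stated. At 6.5 months the error is lower than stated.

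Two assumptions carry this. The simulated control hazard is inferred, not stated. Weight is read as equivalent events; weights from 5 to 20 give 12% to 7% at 6.5 months and 18% to 24% at 8.9. The reproduction is close but not exact: strong-prior power is about 2 points low at the 100-death cut and agrees at the 104-week cut.

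**What to change.** In protocol 12.1 and SAP 5.2:
- Convert the two trial hazards and the prior mean in calendar months (about 0.0245, 0.0181 and 0.0198 per week).
- State the true control hazard used in the simulations and define the prior weight.
- Rerun the simulations and give strong-prior type I error and power as a range over the control medians in protocol Table JBAS.5.1. With the corrected prior, expect type I error of about 7% at 6.5 months, 14% at 8.2 and 16% to 17% at 8.8 to 8.9, and power of about 72% to 84%.
- If 0.0216 is kept, state about 9% to 20% instead. The two sets of figures must not be mixed.

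Adding the third dataset is optional and should be justified either way. With a mean of 0.0191, type I error is about 6% to 15%, and power is about 3 to 6 points below that with 0.0216.

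The cost is a simulation rerun, which should also cover the interim tables that use the same prior, and about 2 to 4 points of strong-prior power at a given control median. No patient procedure changes.

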**Table JBAS.12.2. Simulation Results for Final Analysis**

N (Deaths)	Control Rate Prior	Timing of Analysis	Type I Error	Posterior Probability (HR <1) > 0.84
120 (100)	Strong prior for final analysis	FPV + 32.7 months	14%	83%
120 (100)	Weak prior for final analysis	FPV + 32.7 months	15%	74%

Abbreviations: FPV = first patient visit; HR = hazard ratio.

## 12.2. Statistical and Analytical Plans

### 12.2.1. General Considerations

Statistical analysis of this study will be the responsibility of Eli Lilly and Company.

All patients who receive at least 1 dose of study drug will be evaluated for safety, efficacy, toxicity, and progressive disease endpoints. The progressive disease responses will especially focus on the AFP kinetics and the TGF- $\beta$ 1 levels but also include the assessments of EMT-associated markers (for example, E-cadherin) and fibrosis-related blood markers.

Patients with measurable disease will be included in summaries of tumor response. Tumor response will only be tabulated for patients who received at least 1 dose of study drug and have measurable disease at baseline.

Safety analyses will be based on the safety population, defined as all randomized patients receiving at least 1 dose of any study drug. Patients will be grouped according to treatment received in Cycle 1.

Patients from all sites will be pooled for the purposes of analysis. Inference about survival will be made using a Bayesian posterior probability for the superiority of LY2157299 plus sorafenib arm survival over sorafenib plus placebo arm. The remaining analyses of this study will estimate differences between arms where appropriate, including exploratory analyses.

Results of descriptive analyses and estimates from inferential analyses will be presented by treatment arm. For continuous variables, summary statistics will include number of patients, mean, median, standard deviation, minimum, and maximum. Categorical endpoints will be summarized using number of patients, frequency, and percentages. Any missing longitudinal data will not be imputed, but rather will be estimated from an appropriate random mixed-effects model. Transformations will be applied where assumptions behind any analysis are better satisfied by data being transformed onto an alternative scale. All results from any of these

analyses will be back transformed to the original scale. Alternatively, nonparametric methods will be applied.

Any change to the data-analysis methods described in the protocol will require an amendment ONLY if it changes a principal feature of the protocol. Any other change to the data-analysis methods described in the protocol, and the justification for making the change, will be described in the clinical study report. Additional exploratory analyses of the data will be conducted as deemed appropriate.

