#### **10.1.2. Primary Efficacy Measure**

The primary efficacy endpoint is OS, defined as the time from the date of randomization to the date of death from any cause. For patients not known to have died as of the data cut-off date, OS time will be censored at the last contact date the patient was known to be alive prior to the cut-off date.

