6.1. General Considerations

This plan describes a priori statistical analyses for efficacy and safety that will be performed according to Protocol version 1.0 dated November 18, 2013. Additional exploratory analyses of the data not described in this plan will be conducted as deemed appropriate.

Statistical analysis of this study will be responsibility of both Quintiles (under the direction of Eli Lilly and Company [Lilly]) and Lilly.

The interpretation of the study results will be the responsibility of the investigator with the Lilly Clinical Research Physician (CRP), pharmacokineticist, and statistician.

Patients from all sites will be pooled for the purposes of analysis. Inference about survival will be made using a Bayesian posterior probability for the superiority of LY2157299 plus sorafenib arm survival over sorafenib plus placebo arm. The remaining analyses of this study will estimate differences between arms where appropriate, including exploratory analyses. Descriptive statistics by treatment arm will also be provided.

Results of descriptive analyses and estimates from inferential analyses will be presented by treatment arm. For continuous variables, summary statistics will include number of patients, mean, median, standard deviation, minimum, and maximum. Categorical endpoints will be summarized using number of patients, frequency, and percentages. Any missing longitudinal data will not be imputed, but rather will be estimated from an appropriate random mixed-effects model. Transformations will be applied where assumptions behind any analysis are better satisfied by data being transformed onto an alternative scale. All results from any of these analyses will be back transformed to the original scale. Alternatively, nonparametric methods will be applied.

Any change to the data-analysis methods described in the protocol will require an amendment ONLY if it changes a principal feature of the protocol. Any other change to the data-analysis methods described in the protocol, and the justification for making the change, will be described in the clinical study report. Additional exploratory analyses of the data will be conducted as deemed appropriate.

The following terms and data handling conventions defined in [Table JBAS.6.1](#) will be used in the analysis.

Table JBAS.6.1. Data Handling Conventions

Term	Definitions or Rule
Entered	Patients who have signed the informed consent document directly.

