Screen failures	Patients who have signed informed consent, do not meet eligibility criteria and are not treated/randomized.
Randomized	Patients who have been assigned to study treatment but may have not received any study treatment (LY2157299, LY2157299-matched placebo, or sorafenib).
Patients on therapy	Patients who have been randomized to study treatment and have received at least 1 dose of study treatment (LY2157299, LY2157299-matched placebo, or sorafenib).
Study day	If assessment is on or after date of first treatment dose then (date of assessment) – (date of first study treatment dose) + 1 If assessment precedes first treatment dose then (date of assessment) – (date of first study treatment dose) There is no study day 0. Study day 1 is the date of first dose and study day -1 is the day before the first dose.
Cycle day	If assessment is on or after date of first treatment dose then (date of assessment) – (date of first study treatment dose in cycle) + 1 If assessment precedes first treatment dose then (date of assessment) – (date of first study treatment dose in cycle) There is no cycle day 0. Cycle day 1 is the date of first dose in the cycle and cycle day -1 is the day before the first dose.
Baseline	For change from baseline analysis, baseline value is defined as the last reported measure on or before the first dose date (or discontinuation, if no treatment is given). For change from baseline within a cycle, the measure prior to the first dose if that cycle is baseline.
Study treatment period	Time from treatment start to discontinuation from study treatment
Post-discontinuation – short-term follow-up	The short term follow-up period begins 1 day after discontinuation of study treatment and lasts approximately 30 days (Visit 801).
Post-discontinuation – long-term follow-up	The long-term follow-up period begins 1 day after the short-term follow-up period (Visit 801) is completed and continues until death to collect survival data.

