6.1.1. Analysis Populations

The following populations used for analysis are defined in [Table JBAS.6.2](#) below.

Table JBAS.6.2. Populations used for Analysis

Population	Definitions or Rule
Randomized	Patients who have been randomized to study treatment. Patients in this set will be grouped according to their allocated treatment. All subject characteristics and efficacy analyses (except tumor response) will be conducted on this population.
Per-protocol	Patients who have been randomized to study treatment and did not have any major protocol deviations. Patients in this set will be grouped according to their allocated treatment. Efficacy analyses might be conducted on this population in addition to the randomized population.
Tumor response qualified	Patients who have been randomized to study treatment, received at least 1 dose of study treatment (LY2157299, LY2157299-matched placebo, or sorafenib), had measurable disease at baseline and had at least one baseline and one study treatment period tumor assessment. Tumor response analyses (Section 6.9.2.2) will be conducted on this population. Patients in this set will be grouped according to their allocated treatment, and then the analysis will be repeated using the actual treatment assignment.
Safety	Patients who have been randomized to study treatment and have received at least 1 dose of study treatment (LY2157299, LY2157299-matched placebo, or sorafenib). Patients will be grouped according to actual treatment received in Cycle 1. Safety analyses and efficacy analyses as specified in Section 6.9.2.1 will be performed on this population.

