6.9.2. Secondary Efficacy Analyses/Outcomes/Comparisons

6.9.2.1. Additional Analyses of the Primary Outcome

The same Bayesian analysis as described in Section 6.9.1 will be repeated using the weak prior. The same Bayesian analysis will also be carried out to provide the hazard rates and ratios including 90% predictive intervals of the HR between LY2157299 monotherapy and sorafenib plus placebo therapy.

In addition to the above primary Bayesian analyses for OS, OS curves for each treatment arm will also be analyzed using the Kaplan-Meier product-limit method (Kaplan and Meier 1958). Two-sided, 95% CIs for median OS will be computed by the Brookmeyer and Crowley method (Brookmeyer and Crowley 1982). OS rates at 6 and 12 months will also be estimated using Kaplan-Meier estimates on the OS curve for each treatment arm. Associated 2-sided 95% CIs will also be calculated. Kaplan Meier plots of survival for each treatment group will also be provided.

Pairwise HRs along with 95% CIs between the 3 arms will be estimated using a stratified univariate proportional hazards (PH) model. Additional exploratory analyses using a PH model to control for other factors may be performed, including, but not limited to, ECOG performance status, portal vein thrombosis (yes vs. no), extra hepatic spread (yes vs. no), baseline AFP levels (<200 vs. ≥ 200 , <400 vs. ≥ 400), etiology and TGF- β levels (<3400 pg/ml vs. ≥ 3400 pg/ml). A stepwise procedure for variable selection will be applied. The univariate and multivariate analyses using PH models will be repeated on the safety population (Section 6.1.1) to explore the actual drug effect.

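### Protocol and SAP name different efficacy populations: the SAP settles OS on all randomised patients, but contradicts itself for TTP and PFS

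*Protocol*

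**What the plan says.** **Protocol.** Section 12.2.1 reads: "All patients who receive at least 1 dose of study drug will be evaluated for safety, efficacy, toxicity, and progressive disease endpoints". It then defines a safety population formally, but no efficacy population. Section 10.1.2 makes OS the primary efficacy endpoint, "defined as the time from the date of randomization to the date of death from any cause". Section 12.2.6, the primary analysis, repeats the randomisation start and names no analysis set. Table JBAS.10.1 also times TTP and PFS from randomisation.

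**SAP.** Table JBAS.6.1 describes the randomised group as "Patients who have been assigned to study treatment but may have not received any study treatment". Table JBAS.6.2 says of the randomised population, grouped by allocation: "All subject characteristics and efficacy analyses (except tumor response) will be conducted on this population". Section 6.9.1 (primary analysis) names no population, so the table governs. Section 6.9.2.1 says the proportional hazards models for OS "will be repeated on the safety population (Section 6.1.1) to explore the actual drug effect". Section 6.9.2.2 covers TTP, PFS and response, and closes by assigning all of its analyses to the Tumor Response Qualified Population.

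**Dates.** SAP version 2 was approved on 26 July 2017, before primary database lock, and is written "according to Protocol version 1.0 dated November 18, 2013". Protocol amendment (a) was approved on 18 December 2017 and still carries the 12.2.1 sentence.

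**The concern.** An endpoint timed from randomisation should be analysed in everyone randomised. Requiring a first dose conditions on something that happens after allocation, and requiring an on-treatment tumour assessment conditions on surviving and staying on treatment until one is made. Both documents foresee randomised patients who are never dosed: SAP Table JBAS.6.1, quoted above, and Protocol 7.3.1, which covers randomised patients who discontinue whether or not they took study drug.

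Two things are at stake. For OS, the protocol's only statement about who is evaluated for efficacy differs from the SAP's. For TTP and PFS, the SAP contains two incompatible instructions, and a programmer following 6.9.2.2 would use the more selective one. Arm 1 is open label and contains no sorafenib, so withdrawal between assignment and first dose could differ from the sorafenib arms. That matters most for the monotherapy comparisons.

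**Working it through.** **1. The texts side by side**

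| Endpoint | Protocol | SAP Table JBAS.6.2 | SAP analysis section |
|---|---|---|---|
| OS | dosed patients (12.2.1); 12.2.6 silent | all randomised | 6.9.1 silent; 6.9.2.1 repeats PH models on the safety set |
| TTP, PFS | dosed patients (12.2.1) | all randomised | 6.9.2.2: tumour-response set |
| ORR | dosed, measurable disease | tumour-response set | 6.9.2.2: tumour-response set |

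OS conflicts between the documents. TTP and PFS conflict within the SAP as well.

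**2. Reproducing the plan's power**

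Inputs (Protocol 12.1): 60 combination and 30 control patients, HR 0.667, one-sided alpha 0.14, control hazard 0.0216/week, accrual 1.7/week, about 100 deaths over three arms, success if Pr(HR<1) > 0.84.

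Log-rank power = Φ(√(d·(2/3)(1/3))·|ln 0.667| − z₀.₈₆), where d is deaths in the two arms. With d = 78: √(78 × 2/9) = 4.163; 4.163 × 0.405 = 1.686; 1.686 − 1.080 = 0.606; Φ = 72.8%. The plan states 73%. At exactly 100 total deaths d is 73.3 and power is 71.0%. With 104 weeks' minimum follow-up d is 78.7 to 80.0 and power is 73.0% to 73.5%.

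Bayesian power was simulated 40,000 times with a gamma-exponential model. Prior weight was read as pseudo-deaths and the prior on the treated arm was flat (both assumptions).

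| | Stated | At 100 deaths | At 104 weeks |
|---|---|---|---|
| Strong prior | 83% | 80.9% | 83.7% |
| Weak prior | 74% | 74.6% | 77.8% |

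Type I error came to 13.3%–13.5% (strong) and 15.3%–15.5% (weak), against 14% and 15% stated.

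**3. Dropping undosed patients from OS**

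The documents give no never-dosed rate. Assume 0% to 10%, equal across arms and unrelated to prognosis, with the cut at 100 deaths among all randomised (log-rank from 78 deaths).

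| Never dosed | Patients left | Log-rank | Strong prior | Weak prior |
|---|---|---|---|---|
| 0% | 120 | 72.8% | 80.9% | 74.6% |
| 2% | 118 | 72.2% | 80.7% | 74.4% |
| 5% | 114 | 71.3% | 80.0% | 73.4% |
| 10% | 108 | 69.8% | 78.9% | 72.3% |

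The strong-prior loss is 0.9 points at 5% and 2.0 points at 10%. Type I error stays at about 13% to 15%. This shows lost precision only; it does not show bias from selective exclusion.

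**4. One very early death excluded**

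At 100 deaths the model expects 26.7 control and 46.6 combination deaths. With prior weight 10 the control posterior rests on 36.7 events.

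- SD of log HR = √(1/36.7 + 1/46.6) = 0.221. The normal density at the 0.84 point (z = 0.994) is 0.243.
- One control death with almost no follow-up removed: (1/36.7)/0.221 × 0.243 = 0.030, downward.
- One such combination death removed: (1/46.6)/0.221 × 0.243 = 0.024, upward.
- One in each arm: 0.030 − 0.024 = 0.006, downward.
- Two combination and one control (the 2:1 allocation): 2 × 0.024 − 0.030 = about 0.018, upward.

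An exact gamma calculation starting from 0.84 gives 0.806 after losing the control death and 0.862 after losing the combination death. With prior weight 1 the values are 0.798 and 0.860.

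**5. TTP and PFS**

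The tumour-response set needs a dose, measurable baseline disease and at least one tumour assessment in the study treatment period. The first scheduled on-treatment scan is Cycle 2 Day 14, day 28 + 14 = 42, or 6 weeks. Under the plan's constant hazards the expected proportion dead by then is:

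- Control: 1 − exp(−0.0216 × 6) = 12.2%, or 30 × 0.122 = 3.6 patients.
- Combination: 1 − exp(−0.0216 × 0.667 × 6) = 8.3%, or 60 × 0.083 = 5.0 patients.

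Each of these deaths is a PFS event under SAP 6.9 (absent earlier post-discontinuation therapy), yet patients without an on-treatment assessment leave the analysis. Patients who stop treatment before the scan are lost too, including those whose progression is found in follow-up. The counts are illustrative: eligibility (Child-Pugh A, ECOG ≤ 1) may make early hazard lower, and a physical assessment of palpable or visible tumour could qualify some patients sooner. TTP is less affected by early deaths, because a patient who dies unscanned is censored anyway.

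**The case against.** The strongest reply is that Protocol 12.2.1 is a general evaluability sentence. It says dosed patients will be evaluated; it does not say only they will be. Where the drafters restrict, as for tumour response in the next paragraph, they say so. Other protocol text leans towards all randomised: the success rule in 12.1 counts 120 patients, and 10.1 follows all patients for progression and OS. The SAP then fixes the randomised set for OS before lock. This stands, and it makes the OS part a matter of aligning wording.

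Three stronger readings do not stand.

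- A reader might infer from the approval dates that the sponsor chose the dosed-patient rule after the SAP. Amendment (a) concerns extension-period scheduling and cardiac monitoring; its change list does not touch 12.2.1, so the sentence was carried forward. Updating the SAP's protocol reference would change no result.
- A reader might infer that the OS population remains open until unblinding. The pre-lock SAP closes that choice if it is followed.
- A reader might take the 3-point shift as the expected effect. It needs one almost immediate undosed control death with no counterpart in the combination arm, and it makes the combination look worse. Arms 2 and 3 both receive sorafenib and are blinded to LY2157299 or placebo, so loss before first dose should be roughly balanced between them.

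None of this answers the TTP and PFS contradiction. Table JBAS.6.2 exempts only tumour response, while 6.9.2.2 moves the whole section to the tumour-response set.

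**Conclusion.** Wrong as written: the analysis populations contradict each other. For OS, the protocol's only efficacy-population wording is dosed patients, while the SAP specifies all randomised and governs in practice. Expected harm to the primary comparison is small, provided that never-dosed rates are low and similar in Arms 2 and 3. A borderline posterior probability could still turn on one patient, in either direction.

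For TTP and PFS the SAP does not settle the matter, and the set named in 6.9.2.2 excludes patients on post-randomisation grounds. Bias is a greater risk there and in any comparison with open-label Arm 1, though the documents give no data from which to size it. The monotherapy OS hazard ratio is a secondary estimate with no success rule, and Table JBAS.6.2 already assigns it to the randomised set.

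**What to change.** 1. In Protocol 12.2.1 and 12.2.6, state that OS is analysed in all randomised patients by allocated arm.
2. Repeat that in SAP 6.9.1.
3. In SAP 6.9.2.2, put TTP and PFS on the randomised population and limit the tumour-response set to ORR and DCR. Say how patients with no post-baseline tumour assessment are handled, for example censored at randomisation, with an unscanned death still a PFS event subject to the existing rule on new anticancer therapy.
4. Label any efficacy analysis on dosed patients as sensitivity. In the safety row of SAP Table JBAS.6.2, narrow the pointer to 6.9.2.1 to the proportional hazards repeat; as written it also takes in the weak-prior and monotherapy Bayesian analyses.

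The cost is a few sentences in each document and a changed population flag for the TTP and PFS tables. No new data are needed and no sample-size figure changes.
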